9.10.3. Analysis of Secondary End Points

Table 3. 1: Summary statistics of EQ-5D-5L¹ dimensions and levels, by treatment arm (CHRONOS-A)*

Focal					
	Mobility	Self-care	Usual activities	Pain/discomfort	Anxiety/depression
	n (%)	n (%)	n (%)	n (%)	n (%)
Level 1	xxx (xx%)	xxx (xx%)	xxx (xx%)	xxx (xx%)	xxx (xx%)
Level 2	xxx (xx%)	xxx (xx%)	xxx (xx%)	xxx (xx%)	xxx (xx%)
Level 3	xxx (xx%)	xxx (xx%)	xxx (xx%)	xxx (xx%)	xxx (xx%)
Level 4	xxx (xx%)	xxx (xx%)	xxx (xx%)	xxx (xx%)	xxx (xx%)
Level 5	xxx (xx%)	xxx (xx%)	xxx (xx%)	xxx (xx%)	xxx (xx%)
Total	xxx (xx%)	xxx (xx%)	xxx (xx%)	xxx (xx%)	xxx (xx%)
Radical					
	Mobility	Self-care	Usual activities	Pain/discomfort	Anxiety/depression
	n (%)	n (%)	n (%)	n (%)	n (%)
Level 1	xxx (xx%)	xxx (xx%)	xxx (xx%)	xxx (xx%)	xxx (xx%)
Level 2	xxx (xx%)	xxx (xx%)	xxx (xx%)	xxx (xx%)	xxx (xx%)
Level 3	xxx (xx%)	xxx (xx%)	xxx (xx%)	xxx (xx%)	xxx (xx%)
Level 4	xxx (xx%)	xxx (xx%)	xxx (xx%)	xxx (xx%)	xxx (xx%)
Level 5	xxx (xx%)	xxx (xx%)	xxx (xx%)	xxx (xx%)	xxx (xx%)
Total	xxx (xx%)	xxx (xx%)	xxx (xx%)	xxx (xx%)	xxx (xx%)

^{*}Repeat for all time points (screening, 3 months)

Table 3. 2: Summary statistics for EQ VAS (EQ-5D-5L)¹, by treatment arm (CHRONOS-A)*

	Statistics	Focal	Radical	Total
EQ VAS	N	XXX	XXX	xxx
	Mean (SD)	xx.xx (xx.xx)	xx.xx (xx.xx)	xx.xx (xx.xx)
	Median (IQR)	xx.xx (xx.xx to xx.xx)	xx.xx (xx.xx to xx.xx)	xx.xx (xx.xx to xx.xx)
	Missing – n (%)	xx (xx%)	xx (xx%)	xx (xx%)

^{*}Repeat for all time points (screening, 3 months)

¹See Appendix 2 for details

¹See Appendix 2 for details

mperial Clinic	al
Trials Unit	

Table 3. 3: Summary statistics of IIEF15¹ domains, by treatment arm (CHRONOS-A)*

IIEF15 Domains	Statistics	Focal	Radical	Total
Erectile	N	VOV	VOV	you.
		XXX	xxx	xxx
Function ¹	Mean (SD)	xx.xx (xx.xx)	xx.xx (xx.xx)	xx.xx (xx.xx)
	Median (IQR)	xx.xx (xx.xx to xx.xx)	xx.xx (xx.xx to xx.xx)	xx.xx (xx.xx to xx.xx)
	Missing – n (%)	xx (xx%)	xx (xx%)	xx (xx%)
Orgasmic	N	XXX	XXX	XXX
Function ²	Mean (SD)	xx.xx (xx.xx)	xx.xx (xx.xx)	xx.xx (xx.xx)
	Median (IQR)	xx.xx (xx.xx to xx.xx)	xx.xx (xx.xx to xx.xx)	xx.xx (xx.xx to xx.xx)
	Missing – n (%)	xx (xx%)	xx (xx%)	xx (xx%)
Sexual	N	XXX	XXX	xxx
Desire ³	Mean (SD)	xx.xx (xx.xx)	xx.xx (xx.xx)	xx.xx (xx.xx)
	Median (IQR)	xx.xx (xx.xx to xx.xx)	xx.xx (xx.xx to xx.xx)	xx.xx (xx.xx to xx.xx)
	Missing – n (%)	xx (xx%)	xx (xx%)	xx (xx%)
Intercourse	N	xxx	XXX	XXX
Satisfaction ⁴	Mean (SD)	xx.xx (xx.xx)	xx.xx (xx.xx)	xx.xx (xx.xx)
	Median (IQR)	xx.xx (xx.xx to xx.xx)	xx.xx (xx.xx to xx.xx)	xx.xx (xx.xx to xx.xx)
	Missing – n (%)	xx (xx%)	xx (xx%)	xx (xx%)
Overall	N	XXX	XXX	XXX
Satisfaction ⁵	Mean (SD)	xx.xx (xx.xx)	xx.xx (xx.xx)	xx.xx (xx.xx)
	Median (IQR)	xx.xx (xx.xx to xx.xx)	xx.xx (xx.xx to xx.xx)	xx.xx (xx.xx to xx.xx)
	Missing – n (%)	xx (xx%)	xx (xx%)	xx (xx%)

^{*}Repeat for all time points (screening, 3 months)

Table 3. 4: Summary statistics of EPIC-26¹ domains, by treatment arm (CHRONOS-A)*

EPIC-26	Statistics	Focal	Radical	Total
Domains				
Urinary	N	XXX	XXX	XXX
Incontinence	Mean (SD)	xx.xx (xx.xx)	xx.xx (xx.xx)	xx.xx (xx.xx)
	Median (IQR)	xx.xx (xx.xx to xx.xx)	xx.xx (xx.xx to xx.xx)	xx.xx (xx.xx to xx.xx)
	Missing – n (%)	xx (xx%)	xx (xx%)	xx (xx%)
Urinary	N	xxx	xxx	XXX
Irritative/	Mean (SD)	xx.xx (xx.xx)	xx.xx (xx.xx)	xx.xx (xx.xx)
Obstructive	Median (IQR)	xx.xx (xx.xx to xx.xx)	xx.xx (xx.xx to xx.xx)	xx.xx (xx.xx to xx.xx)
	Missing – n (%)	xx (xx%)	xx (xx%)	xx (xx%)
Bowel	N	xxx	xxx	xxx
	Mean (SD)	xx.xx (xx.xx)	xx.xx (xx.xx)	xx.xx (xx.xx)
	Median (IQR)	xx.xx (xx.xx to xx.xx)	xx.xx (xx.xx to xx.xx)	xx.xx (xx.xx to xx.xx)
	Missing – n (%)	xx (xx%)	xx (xx%)	xx (xx%)
Sexual	N	XXX	XXX	XXX
	Mean (SD)	xx.xx (xx.xx)	xx.xx (xx.xx)	xx.xx (xx.xx)
	Median (IQR)	xx.xx (xx.xx to xx.xx)	xx.xx (xx.xx to xx.xx)	xx.xx (xx.xx to xx.xx)
	Missing – n (%)	xx (xx%)	xx (xx%)	xx (xx%)
Hormonal	N	XXX	XXX	XXX
	Mean (SD)	xx.xx (xx.xx)	xx.xx (xx.xx)	xx.xx (xx.xx)
	Median (IQR)	xx.xx (xx.xx to xx.xx)	xx.xx (xx.xx to xx.xx)	xx.xx (xx.xx to xx.xx)
	Missing – n (%)	xx (xx%)	xx (xx%)	xx (xx%)

^{*}Repeat for all time points (screening, 3 months)

¹See Appendix 2 for details

¹See Appendix 2 for details

STATISTICAL ANALYSIS PLAN: FEASIBILITY

Table 3. 5: Summary statistics of EPIC-URINARY DOMAIN 1 subscales, by treatment arm (CHRONOS-A) *

EPIC-URINARY	Statistics	Focal	Radical	Total
DOMAIN subscales				
Function	N	XXX	XXX	XXX
	Mean (SD)	xx.xx (xx.xx)	xx.xx (xx.xx)	xx.xx (xx.xx)
	Median (IQR)	xx.xx (xx.xx to	xx.xx (xx.xx to	xx.xx (xx.xx to
	Missing – n (%)	xx.xx)	xx.xx)	xx.xx)
		xx (xx%)	xx (xx%)	xx (xx%)
Bother	N	XXX	XXX	XXX
	Mean (SD)	xx.xx (xx.xx)	xx.xx (xx.xx)	xx.xx (xx.xx)
	Median (IQR)	xx.xx (xx.xx to	xx.xx (xx.xx to	xx.xx (xx.xx to
	Missing – n (%)	xx.xx)	xx.xx)	xx.xx)
		xx (xx%)	xx (xx%)	xx (xx%)
Incontinence	N	XXX	XXX	XXX
	Mean (SD)	xx.xx (xx.xx)	xx.xx (xx.xx)	xx.xx (xx.xx)
	Median (IQR)	xx.xx (xx.xx to	xx.xx (xx.xx to	xx.xx (xx.xx to
	Missing – n (%)	xx.xx)	xx.xx)	xx.xx)
		xx (xx%)	xx (xx%)	xx (xx%)
Irritative/Obstructive	N	XXX	XXX	XXX
	Mean (SD)	xx.xx (xx.xx)	xx.xx (xx.xx)	xx.xx (xx.xx)
	Median (IQR)	xx.xx (xx.xx to	xx.xx (xx.xx to	xx.xx (xx.xx to
	Missing – n (%)	xx.xx)	xx.xx)	xx.xx)
		xx (xx%)	xx (xx%)	xx (xx%)

^{*}Repeat for all time points (screening, 3 months)

¹See Appendix 2 for details

Table 3. 6: Summary statistics of EQ-5D-5L¹ dimensions and levels, by treatment arm (CHRONOS-B)*

Focal alor	ne				
	Mobility	Self-care	Usual activities	Pain/discomfort	Anxiety/depression
	n (%)	n (%)	n (%)	n (%)	n (%)
Level 1	xxx (xx%)	xxx (xx%)	xxx (xx%)	xxx (xx%)	xxx (xx%)
Level 2	xxx (xx%)	xxx (xx%)	xxx (xx%)	xxx (xx%)	xxx (xx%)
Level 3	xxx (xx%)	xxx (xx%)	xxx (xx%)	xxx (xx%)	xxx (xx%)
Level 4	xxx (xx%)	xxx (xx%)	xxx (xx%)	xxx (xx%)	xxx (xx%)
Level 5	xxx (xx%)	xxx (xx%)	xxx (xx%)	xxx (xx%)	xxx (xx%)
Total	xxx (xx%)	xxx (xx%)	xxx (xx%)	xxx (xx%)	xxx (xx%)
Focal + fin	asteride				
	Mobility	Self-care	Usual activities	Pain/discomfort	Anxiety/depression
	n (%)	n (%)	n (%)	n (%)	n (%)
Level 1	xxx (xx%)	xxx (xx%)	xxx (xx%)	xxx (xx%)	xxx (xx%)
Level 2	xxx (xx%)	xxx (xx%)	xxx (xx%)	xxx (xx%)	xxx (xx%)
Level 3	xxx (xx%)	xxx (xx%)	xxx (xx%)	xxx (xx%)	xxx (xx%)
Level 4	xxx (xx%)	xxx (xx%)	xxx (xx%)	xxx (xx%)	xxx (xx%)
Level 5	xxx (xx%)	xxx (xx%)	xxx (xx%)	xxx (xx%)	xxx (xx%)
Total	xxx (xx%)	xxx (xx%)	xxx (xx%)	xxx (xx%)	xxx (xx%)
Focal + bio	alutimide				
	Mobility	Self-care	Usual activities	Pain/discomfort	Anxiety/depression
	n (%)	n (%)	n (%)	n (%)	n (%)
Level 1	xxx (xx%)	xxx (xx%)	xxx (xx%)	xxx (xx%)	xxx (xx%)
Level 2	xxx (xx%)	xxx (xx%)	xxx (xx%)	xxx (xx%)	xxx (xx%)
Level 3	xxx (xx%)	xxx (xx%)	xxx (xx%)	xxx (xx%)	xxx (xx%)
Level 4	xxx (xx%)	xxx (xx%)	xxx (xx%)	xxx (xx%)	xxx (xx%)
Level 5	xxx (xx%)	xxx (xx%)	xxx (xx%)	xxx (xx%)	xxx (xx%)
Total	xxx (xx%)	xxx (xx%)	xxx (xx%)	xxx (xx%)	xxx (xx%)

^{*}Repeat for all time points (screening, 3 months)

Table 3. 7: Summary statistics for EQ VAS (EQ-5D-5L)¹, by treatment arm (CHRONOS-B)*

	Statistics	Focal alone	Focal + finasteride	Focal + bicalutimide	Total
EQ VAS	N Mean (SD) Median (IQR) Missing – n (%)	xxx xx.xx (xx.xx) xx.xx (xx.xx to xx.xx) xx (xx%)			

^{*}Repeat for all time points (screening, 3 months)

¹See Appendix 2 for details

¹See Appendix 2 for details

Imperial Clinical
Trials Unit

STATISTICAL ANALYSIS PLAN: FEASIBILITY

Table 3. 8: Summary statistics of IIEF15¹ domains, by treatment arm (CHRONOS-B)*

IIEF15 Domains	Statistics	Focal alone	Focal +	Focal +	Total
			finasteride	bicalutimide	
Erectile Function	N	XXX	XXX	XXX	XXX
	Mean (SD)	xx.xx (xx.xx)	xx.xx (xx.xx)	xx.xx (xx.xx)	xx.xx (xx.xx)
	Median (IQR)	xx.xx (xx.xx to	xx.xx (xx.xx to	xx.xx (xx.xx	xx.xx (xx.xx
		xx.xx)	xx.xx)	to xx.xx)	to xx.xx)
	Missing – n (%)	xx (xx%)	xx (xx%)	xx (xx%)	xx (xx%)
Orgasmic	N	XXX	XXX	XXX	XXX
Function	Mean (SD)	xx.xx (xx.xx)	xx.xx (xx.xx)	xx.xx (xx.xx)	xx.xx (xx.xx)
	Median (IQR)	xx.xx (xx.xx to	xx.xx (xx.xx to	xx.xx (xx.xx	xx.xx (xx.xx
		xx.xx)	xx.xx)	to xx.xx)	to xx.xx)
	Missing – n (%)	xx (xx%)	xx (xx%)	xx (xx%)	xx (xx%)
Sexual Desire	N	XXX	XXX	XXX	XXX
	Mean (SD)	xx.xx (xx.xx)	xx.xx (xx.xx)	xx.xx (xx.xx)	xx.xx (xx.xx)
	Median (IQR)	xx.xx (xx.xx to	xx.xx (xx.xx to	xx.xx (xx.xx	xx.xx (xx.xx
		xx.xx)	xx.xx)	to xx.xx)	to xx.xx)
	Missing – n (%)	xx (xx%)	xx (xx%)	xx (xx%)	xx (xx%)
Intercourse	N	XXX	XXX	XXX	XXX
Satisfaction	Mean (SD)	xx.xx (xx.xx)	xx.xx (xx.xx)	xx.xx (xx.xx)	xx.xx (xx.xx)
	Median (IQR)	xx.xx (xx.xx to	xx.xx (xx.xx to	xx.xx (xx.xx	xx.xx (xx.xx
		xx.xx)	xx.xx)	to xx.xx)	to xx.xx)
	Missing – n (%)	xx (xx%)	xx (xx%)	xx (xx%)	xx (xx%)
Overall	N	XXX	XXX	XXX	XXX
Satisfaction	Mean (SD)	xx.xx (xx.xx)	xx.xx (xx.xx)	xx.xx (xx.xx)	xx.xx (xx.xx)
	Median (IQR)	xx.xx (xx.xx to	xx.xx (xx.xx to	xx.xx (xx.xx	xx.xx (xx.xx
		xx.xx)	xx.xx)	to xx.xx)	to xx.xx)
	Missing – n (%)	xx (xx%)	xx (xx%)	xx (xx%)	xx (xx%)

^{*}Repeat for all time points (screening, 3 months)

¹See Appendix 2 for details

Imperial Clinical
Trials Unit

Table 3. 9: Summary statistics of EPIC-26¹ domains, by treatment arm (CHRONOS-B)*

EPIC-26 Domains	Statistics	Focal alone	Focal +	Focal +	Total
			finasteride	bicalutimide	
Urinary Incontinence	N	XXX	XXX	XXX	XXX
	Mean (SD)	xx.xx (xx.xx)	xx.xx (xx.xx)	xx.xx (xx.xx)	xx.xx (xx.xx)
	Median (IQR)	xx.xx (xx.xx	xx.xx (xx.xx to	xx.xx (xx.xx	xx.xx (xx.xx
		to xx.xx)	xx.xx)	to xx.xx)	to xx.xx)
	Missing – n (%)	xx (xx%)	xx (xx%)	xx (xx%)	xx (xx%)
Urinary	N	XXX	XXX	XXX	XXX
Irritative/Obstructive	Mean (SD)	xx.xx (xx.xx)	xx.xx (xx.xx)	xx.xx (xx.xx)	xx.xx (xx.xx)
	Median (IQR)	xx.xx (xx.xx	xx.xx (xx.xx to	xx.xx (xx.xx	xx.xx (xx.xx
		to xx.xx)	xx.xx)	to xx.xx)	to xx.xx)
	Missing – n (%)	xx (xx%)	xx (xx%)	xx (xx%)	xx (xx%)
Bowel	N	XXX	XXX	XXX	xxx
	Mean (SD)	xx.xx (xx.xx)	xx.xx (xx.xx)	xx.xx (xx.xx)	xx.xx (xx.xx)
	Median (IQR)	xx.xx (xx.xx	xx.xx (xx.xx to	xx.xx (xx.xx	xx.xx (xx.xx
		to xx.xx)	xx.xx)	to xx.xx)	to xx.xx)
	Missing – n (%)	xx (xx%)	xx (xx%)	xx (xx%)	xx (xx%)
Sexual	N	XXX	XXX	XXX	xxx
	Mean (SD)	xx.xx (xx.xx)	xx.xx (xx.xx)	xx.xx (xx.xx)	xx.xx (xx.xx)
	Median (IQR)	xx.xx (xx.xx	xx.xx (xx.xx to	xx.xx (xx.xx	xx.xx (xx.xx
		to xx.xx)	xx.xx)	to xx.xx)	to xx.xx)
	Missing – n (%)	xx (xx%)	xx (xx%)	xx (xx%)	xx (xx%)
Hormonal	N	XXX	XXX	XXX	XXX
	Mean (SD)	xx.xx (xx.xx)	xx.xx (xx.xx)	xx.xx (xx.xx)	xx.xx (xx.xx)
	Median (IQR)	xx.xx (xx.xx	xx.xx (xx.xx to	xx.xx (xx.xx	xx.xx (xx.xx
		to xx.xx)	xx.xx)	to xx.xx)	to xx.xx)
	Missing – n (%)	xx (xx%)	xx (xx%)	xx (xx%)	xx (xx%)

^{*}Repeat for all time points (screening, 3 months)

Table 3. 10: Summary statistics of EPIC-URINARY DOMAIN 1 subscales, by treatment arm (CHRONOS-B) *

EPIC-URINARY DOMAIN subscales	Statistics	Focal alone	Focal + finasteride	Focal + bicalutimide	Total
Function	N	XXX	XXX	XXX	XXX
	Mean (SD)	xx.xx (xx.xx)	xx.xx (xx.xx)	xx.xx (xx.xx)	xx.xx (xx.xx)
	Median (IQR)	xx.xx (xx.xx	xx.xx (xx.xx to	xx.xx (xx.xx	xx.xx (xx.xx
	, ,	to xx.xx)	xx.xx)	to xx.xx)	to xx.xx)
	Missing – n (%)	xx (xx%)	xx (xx%)	xx (xx%)	xx (xx%)
Bother	N	XXX	XXX	XXX	XXX
	Mean (SD)	xx.xx (xx.xx)	xx.xx (xx.xx)	xx.xx (xx.xx)	xx.xx (xx.xx)
	Median (IQR)	xx.xx (xx.xx	xx.xx (xx.xx to	xx.xx (xx.xx	xx.xx (xx.xx
		to xx.xx)	xx.xx)	to xx.xx)	to xx.xx)
	Missing – n (%)	xx (xx%)	xx (xx%)	xx (xx%)	xx (xx%)
Incontinence	N	XXX	XXX	XXX	xxx
	Mean (SD)	xx.xx (xx.xx)	xx.xx (xx.xx)	xx.xx (xx.xx)	xx.xx (xx.xx)
	Median (IQR)	xx.xx (xx.xx	xx.xx (xx.xx to	xx.xx (xx.xx	xx.xx (xx.xx
		to xx.xx)	xx.xx)	to xx.xx)	to xx.xx)
	Missing – n (%)	xx (xx%)	xx (xx%)	xx (xx%)	xx (xx%)
Irritative/Obstructive	N	XXX	XXX	XXX	xxx
	Mean (SD)	xx.xx (xx.xx)	xx.xx (xx.xx)	xx.xx (xx.xx)	xx.xx (xx.xx)
	Median (IQR)	xx.xx (xx.xx	xx.xx (xx.xx to	xx.xx (xx.xx	xx.xx (xx.xx
		to xx.xx)	xx.xx)	to xx.xx)	to xx.xx)
	Missing – n (%)	xx (xx%)	xx (xx%)	xx (xx%)	xx (xx%)

^{*}Repeat for all time points (screening, 3 months)

¹See Appendix 2 for details

Imperial Clinical Trials Unit STATISTICAL ANALYSIS PLAN: FEASIBILITY

¹See Appendix 2 for details

Imperial Clinical Trials Unit	STATISTICAL ANALYSIS PLAN: FEASIBILITY
----------------------------------	--

9.10.4. Protocol Deviations/Violations

Table 4. 1: Listing of Protocol Deviations and Violations*

Subject ID	Treatme nt Group	Site	Date reported	Deviatio n or violation	How Identified ?	Description	Classification	Date of deviation/ violation	Response

^{*}Report protocol deviations for CHRONOS-A and CHRONOS-B separately

Table 4. 2: Number of Protocol Deviations and Violations*

Type of Deviation/Violation				Total
Inclusion/exclusion criteria	xx (xx%)	xx (xx%)	xx (xx%)	xx (xx%)
Study drug administration	xx (xx%)	xx (xx%)	xx (xx%)	xx (xx%)
Sampling/laboratory measurements	xx (xx%)	xx (xx%)	xx (xx%)	xx (xx%)
Consent issue	xx (xx%)	xx (xx%)	xx (xx%)	xx (xx%)
Study visit windows	xx (xx%)	xx (xx%)	xx (xx%)	xx (xx%)
NIMP administration	xx (xx%)	xx (xx%)	xx (xx%)	xx (xx%)
Study drug prescription	xx (xx%)	xx (xx%)	xx (xx%)	xx (xx%)
Dispensing	xx (xx%)	xx (xx%)	xx (xx%)	xx (xx%)
Accountability	xx (xx%)	xx (xx%)	xx (xx%)	xx (xx%)
Compliance	xx (xx%)	xx (xx%)	xx (xx%)	xx (xx%)
Missed study visit	xx (xx%)	xx (xx%)	xx (xx%)	xx (xx%)
Study measurements/assessments:	xx (xx%):	xx (xx%):	xx (xx%):	xx (xx%):
Primary outcome measure	xx (xx%)	xx (xx%)	xx (xx%)	xx (xx%)
Secondary outcome measure	xx (xx%)	xx (xx%)	xx (xx%)	xx (xx%)
Safety outcome	xx (xx%)	xx (xx%)	xx (xx%)	xx (xx%)
Device	xx (xx%)	xx (xx%)	xx (xx%)	xx (xx%)
Equipment	xx (xx%)	xx (xx%)	xx (xx%)	xx (xx%)
Prohibited medication/substance(s)	xx (xx%)	xx (xx%)	xx (xx%)	xx (xx%)
AE/SAE reporting	xx (xx%)	xx (xx%)	xx (xx%)	xx (xx%)
Blinding/unblinding	xx (xx%)	xx (xx%)	xx (xx%)	xx (xx%)
Randomisation:	xx (xx%):	xx (xx%):	xx (xx%):	xx (xx%):
(Reason for deviation)	xx (xx%)	xx (xx%)	xx (xx%)	xx (xx%)
(Reason for deviation)	xx (xx%)	xx (xx%)	xx (xx%)	xx (xx%)
Implementation of document prior to research approval	xx (xx%)	xx (xx%)	xx (xx%)	xx (xx%)
Licence/certification/calibration/servicing (labs and equipment)	xx (xx%)	xx (xx%)	xx (xx%)	xx (xx%)
Delegation log/authorisation	xx (xx%)	xx (xx%)	xx (xx%)	xx (xx%)
	xx (xx%)	xx (xx%)	xx (xx%)	xx (xx%)

Imperial Clinical Trials Unit	STATISTICAL ANALYSIS PLAN: FEASIBILITY	CHRONOS
----------------------------------	--	---------

Dose interruptions/modifications not specified in				
protocol	xx (xx%)	xx (xx%)	xx (xx%)	xx (xx%)
Variation in clinical management of participant	xx (xx%)	xx (xx%)	xx (xx%)	xx (xx%)
Withdrawal issue	xx (xx%)	xx (xx%)	xx (xx%)	xx (xx%)
Falsifying research or medical records	xx (xx%)	xx (xx%)	xx (xx%)	xx (xx%)
Repeated protocol deviations (of same type)	xx (xx%):	xx (xx%):	xx (xx%):	xx (xx%):
COVID-19 Related:	xx (xx%)	xx (xx%)	xx (xx%)	xx (xx%)
(Please specify)	xx (xx%)	xx (xx%)	xx (xx%)	xx (xx%)
(Please specify)	, ,	, ,	, ,	, ,
Other:	xx (xx%):	xx (xx%):	xx (xx%):	xx (xx%):
	xx (xx%)	xx (xx%)	xx (xx%)	xx (xx%)
	xx (xx%)	xx (xx%)	xx (xx%)	xx (xx%)
	xx (xx%)	xx (xx%)	xx (xx%)	xx (xx%)
	xx (xx%)	xx (xx%)	xx (xx%)	xx (xx%)
Total	xx (xx%)	xx (xx%)	xx (xx%)	xx (xx%)

^{*}Report protocol deviations for CHRONOS-A and CHRONOS-B separately

STATISTICAL ANALYSIS PLAN: FEASIBILITY

CHRONOS

9.11. Figures to present

- Graph displaying recruitment rate over time (CHRONOS-A and CHRONOS-B)
- Graph displaying actual vs target recruitment rate over time (CHRONOS-A and CHRONOS-B)
- Graph displaying randomisation rate over time (CHRONOS-A and CHRONOS-B)
- Kaplan-Meier plots displaying withdrawal over time (CHRONOS-A and CHRONOS-B)
- Histograms of EQ-5D-5L dimensions and levels at each time point for each treatment group (CHRONOS-A and CHRONOS-B)
- Histograms of EQ VAS at each time point for each treatment group (CHRONOS-A and CHRONOS-B)
- Histograms of IIEF15 domains at each time point for each treatment group (CHRONOS-A and CHRONOS-B)
- Histograms of EPIC-26 domains at each time point for each treatment group (CHRONOS-A and CHRONOS-B)
- Histograms of EPIC-URINARY DOMAIN subscales at each time point for each treatment group (CHRONOS-A and CHRONOS-B).

10. Impact of the Covid-19 Pandemic

10.1. Analysis Populations

On 05/03/2020, Covid-19 was added to Public Health England's list of notifiable diseases in England and Wales (11).

Analysis Population	Population Definition	End Points
Patients randomised	Patients randomised to the trial	Baseline demographics
before the Covid-19 pandemic	before 05/03/2020	 Recruitment rate Reasons for ineligibility
 Patients randomised during/after the Covid-19 pandemic 	Patients randomised to the trial on/after 05/03/2020	Time between consent and randomisation
 Patients who underwent radical or focal treatment before the Covid-19 pandemic 	Patients whose radical or focal treatment start date is before 05/03/2020	 Time between randomisation and treatment Treatment compliance
Patients who underwent radical or focal treatment during/after the Covid-19 pandemic	Patients whose radical or focal treatment start date is on/after 05/03/2020	(CHRONOS-A and CHRONOS-B)
Patients who started neoadjuvant drug treatment before the Covid- 19 pandemic	 Patients whose neoadjuvant drug treatment start date is before 05/03/2020 (CHRONO- B only) 	Drug compliance (CHRONOS-B)
 Patients who started neoadjuvant drug treatment during/after the Covid-19 pandemic 	Patients whose neoadjuvant drug treatment start date is on/after 05/03/2020 (CHRONOS-B only)	
Patients who underwent their most recent consecutive visits before the Covid-19 pandemic	 Patients whose most recent date of visit is before 05/03/2020 	Time between consecutive visits
 Patients who underwent their most recent consecutive visits during/after the Covid-19 pandemic 	Patients whose most recent date of visit is on/after 05/03/2020	
 Patients who attended the visit in question before Covid-19 pandemic 	Patients whose date of visit is before 05/03/2020	 Proportions of patients with missing or delayed visits
 Patients who attended the visit in question after the Covid-19 pandemic 	Patients whose date of visit is on/after 05/03/2020	
 Patients who withdrew from the trial before the Covid- 19 pandemic 	Patients whose withdrawal date if before 05/03/2020	Reasons for withdrawal
 Patients who withdrew during/after the Covid-19 pandemic 	Patients whose withdrawal date is on/after 05/03/2020	

The following analyses will only be presented is there exist patients in both the before and during/after Covid-19 pandemic populations. Analyses for populations which do not contain any patients will be omitted as they are already included in the main analysis outlined in Section 9.

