9.5. Impact of the Covid-19 Pandemic

To assess the impact of the Covid-19 pandemic on the feasibility phase of the trial, we will assess the baseline demographics, recruitment rate, randomisation rate, reasons for ineligibility, and time between consent and randomisation to see if there exist important differences between the population recruited before the Covid-19 pandemic and the population recruited during/after the Covid-19 pandemic.

Time between randomisation and treatment, treatment compliance (CHRONOS-A and CHRONOS-B) and drug compliance (CHRONOS-B) will be assessed between the population who

Imperial Clinical
Trials Unit

STATISTICAL ANALYSIS PLAN: FEASIBILITY

CHRONOS

underwent treatment before the Covid-19 pandemic and those who underwent treatment during/after the Covid-19 pandemic.

Time between consecutive visits will be assessed between the population who underwent their most recent consecutive visit before the Covid-19 pandemic and those who underwent their most recent consecutive visit during/after the Covid-19 pandemic. Similarly, proportions of patients with missing or delayed visits will be assessed between patients who underwent that visit before the Covid-19 pandemic and those who underwent that visit during/after the Covid-19 pandemic.

Reasons for withdrawal will be assessed between the population who withdrew before the Covid-19 pandemic and the population who withdrew during/after the Covid-19 pandemic.

Trial processes and conduct will also be assessed for important differences between these populations. This analysis is detailed further in Section Error! Reference source not found.

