10.3. Analysis Summary

End Points	Outcome/Variable	Analysis	Population
Feasibility and	Recorded data on	Mean number of	All randomised
acceptance of	whether patients have	patients recruited per	patients before
randomisation	been (CONSORT):	month per centre	Covid-19
(rate per-month per-centre	RecruitedEnrolled and	Recruitment rate	. All roadonsies d
averaged) and	 Enrolled and consented 	 Graph displaying recruitment rate over 	 All randomised patients during/after
compliance to	Randomised	time	Covid-19
allocated arm	Withdrawn/Lost to	Graph of actual vs	
	follow-up	target recruitment	
	 In follow-up (and 	rate over time	
	what stage of follow-		
	up)	Mean number of	
	Completed	patients randomised per month per centre	
		Randomisation rate	
		Graph displaying	
		randomisation rate	
		over time	
	Days between	Summary statistics for	
	consent and	time between consent and randomisation	
	randomisation	and randomisation	
		Reasons for ineligibility	
	Reasons for Reasons for Reasons fo	,	
	ineligibility		
	 Days between 	Summary statistics for	Patients who started
	randomisation and	time between	treatment before
	start of treatment	randomisation and treatment	Covid-19 • Patients who started
	 Days between randomisation and 	Summary statistics for	Patients who started treatment
	start of neoadjuvant	time between	during/after Covid-
	drug treatment	randomisation and start	19
	(CHRONOS-B)	of neoadjuvant	
	Days between start of	treatment (CHRONOS-	
	neoadjuvant drug treatment and start of	B only) Summary statistics for	
	focal therapy	time between start of	
	(CHRONOS-B)	neoadjuvant treatment	
	Treatment details (as	and start of focal	
	recorded at Visit 2)	therapy (CHRONOS-B	
		only)	
		Treatment compliance:	

Imperial Clinical
Trials Unit

STATISTICAL ANALYSIS PLAN: FEASIBILITY

CHRONOS

 Treatment details (as recorded at Visit 2/3) Protocol deviations for treatment compliance 	 Proportions of patients who underwent their allocated treatment (Visit 2) Drug compliance (CHRONOS-B only): Proportions of patients returned their empty blister packs (yes/no) (recorded at Visit 3) Proportions of patients who were given the drug and do not have a registered protocol deviations stating that the drug was taken for less than 8 weeks 	 Patients who started neoadjuvant drug treatment before Covid-19 (CHRONOS-B only) Patients who started neoadjuvant drug treatment during/after Covid-19 (CHRONOS-B only)

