10.4. Analysis of End Points

The following analyses will be conducted separately for each of the two patient populations defined in the table above (Section 10.3).

STATISTICAL ANALYSIS PLAN: FEASIBILITY

CHRONOS

The mean number of patients recruited and randomised per month, per centre (including only the months in which the centre is open and recruiting), will be calculated. Overall recruitment and randomisation rates will also be calculated, along with their corresponding 95% confidence intervals. Recruitment rate is calculated as the number of participants recruited out of the total number approached. Randomisation rate is calculated as the number of participants randomised out of the total number recruited. Graphs displaying the recruitment and randomisation rates over time will be presented. A graph displaying the actual vs target recruitment rates will also be presented. These analyses will be conducted for CHRONOS-A and CHRONOS-B.

Compliance will be summarised using summary statistics, by treatment arm, for the time between consecutive visits, from screening visit to final follow-up visit (Visit 3 for feasibility phase). The proportions of patients, in each treatment arm, with a missing or delayed visit will also be presented. A missed visit is a visit at which no information was collected. A delayed visit is a visit which is outside of the visit window defined in the Visit Schedule (Section 6.7.2). These statistics will be presented for CHRONOS-A and CHRONOS-B.

Summary statistics for time between consent and randomisation, and randomisation and treatment will be presented by treatment arm. Summary statistics will also be presented for time between consecutive visits, by treatment arm.

For CHRONOS-B only, summary statistics will also be presented for time between randomisation and start of neoadjuvant treatment, and time between start of neoadjuvant treatment and start of focal therapy.

Treatment, for CHRONOS-A and CHRONOS-B, is recorded at Visit 2 (Treatment Visit). For focal therapy arms (CHRONOS-A (Focal arm) and CHRONOS-B) treatment is recorded by date of treatment and completed treatment details at Visit 2. For the radical arm of CHRONOS-A, treatment is recorded by date of visit 2 and completed treatment details on Radiotherapy/Brachytherapy Log and Prostatectomy Log at Visit 2. The proportions of patients in each treatment arm who underwent treatment will be presented, along with their corresponding 95% confidence intervals.

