10.6.2. Analysis of End Points

Table 6. 1: Mean number of patients recruited and randomised per month per centre, for patients recruited to the trial before¹ the Covid-19 pandemic (CHRONOS-A and CHRONOS-B)

See output of Table 2. 2, but for patients recruited to the trial before the Covid-19 pandemic.

¹Patients were recruited before the Covid-19 pandemic if they were recruited to the trial before 05/03/2020 (see Section 10.1)

Table 6. 2: Mean number of patients recruited and randomised per month per centre, for patients recruited to the trial during/after¹ the Covid-19 pandemic (CHRONOS-A and CHRONOS-B)

See output of Table 2. 2, but for patients recruited to the trial during/after¹ the Covid-19 pandemic.

¹Patients were recruited during/after the Covid-19 pandemic if they were recruited to the trial after 05/03/2020 (see Section 10.1)

STATISTICAL ANALYSIS PLAN: FEASIBILITY

CHRONOS

Table 6. 3: Recruitment and randomisation rates¹, for patients recruited to the trial before² the Covid-19 pandemic (CHRONOS-A and CHRONOS-B)

See output for Table 2. 3, but for patients recruited to the trial before² the Covid-19 pandemic.

Table 6. 4: Recruitment and randomisation rates¹, for patients recruited to the trial during/after² the Covid-19 pandemic (CHRONOS-A and CHRONOS-B)

See output for Table 2. 3, but for patients recruited to the trial during/after² the Covid-19 pandemic.

Table 6. 5: Reasons for ineligibility, for patients recruited to the trial before¹ the Covid-19 pandemic (CHRONOS-A and CHRONOS-B)

See output for Table 2. 11, but for patients recruited to the trial before the Covid-19 pandemic.

¹Patients were recruited before the Covid-19 pandemic if they were recruited to the trial before 05/03/2020 (see Section 10.1)

Table 6. 6: Reasons for ineligibility, for patients recruited to the trial during/after¹ the Covid-19 pandemic (CHRONOS-A and CHRONOS-B)

See output for Table 2. 11, but for patients recruited to the trial during/after¹ the Covid-19 pandemic.

¹Patients were recruited during/after the Covid-19 pandemic if they were recruited to the trial after 05/03/2020 (see Section 10.1)

Table 6. 7: Reasons for withdrawal, for patients who withdrew from the trial before¹ the Covid-19 pandemic (CHRONOS-A and CHRONOS-B)

See output for Table 2. 12, but for patients who withdrew from the trial before the Covid-19 pandemic.

¹Patients were recruited before the Covid-19 pandemic if they were recruited to the trial before 05/03/2020 (see Section 10.1)

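### The SAP's Covid-19 comparison sets recruitment rate and ineligibility within randomised or recruited men but divides by men approached, and gives no rule for dating men never recruited

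*SAP*

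**What the plan says.** SAP 9.5 states the purpose. It will compare baseline demographics, "recruitment rate, randomisation rate, reasons for ineligibility, and time between consent and randomisation" between men recruited before the pandemic and men recruited during or after it.

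The populations are then set in three places:

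- SAP 10.1 defines the later group as "Patients randomised to the trial on/after 05/03/2020", with a matching earlier group. The end points listed against this pair include "Recruitment rate Reasons for ineligibility" (two adjacent entries). Randomisation rate is not listed there.
- SAP 10.3 lists recruitment rate, randomisation rate and reasons for ineligibility against populations that begin "All randomised", one for each period. SAP 10.4 opens by tying its calculations to these populations.
- SAP 10.6.2 titles Tables 6.3 to 6.6 by recruited men. Table 6.5, for example, begins "Reasons for ineligibility, for patients recruited to the trial before".

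The denominators are set separately. SAP 10.4 says: "Recruitment rate is calculated as the number of participants recruited out of the total number approached". It also says: "Randomisation rate is calculated as the number of participants randomised out of the total number recruited". The footnote to Tables 6.3 and 6.4, carried over from Table 2.3, puts both rates over the number of people approached.

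The main analysis differs. SAP Section 7 and the summary table in 9.2 include every man approached as well as every man randomised.

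**The concern.** A recruitment rate needs the men who said no, and a table of ineligibility reasons needs the men who were turned away. No population defined in Section 10 for these end points contains a man who was approached and declined, or who was excluded before consent. The populations and the denominator therefore pull in different directions, and the analyst has to decide which to follow.

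What is at stake is the planned evidence on whether acceptance or eligibility changed after 05/03/2020. If the pilot recruits poorly, readers will look here to see whether the shortfall came with the pandemic or was present from the start.

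**Working it through.** **The plan's own figure.** The only number that the SAP gives for recruitment rate is in Section 11: 33% with n = 60, 95% CI (0.211, 0.449). The Wald formula gives 0.33 ± 1.96 × √(0.33 × 0.67 / 60) = 0.33 ± 0.119 = (0.211, 0.449). It reproduces, but it is not split by period and does not bear on this point.

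**Assumed counts.** The documents give no counts by period, so two scenarios are assumed. They are scaled so that about 60 men recruited at 33% implies 60 / 0.33 ≈ 182 approached.

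| Scenario | Period | Approached | Recruited | Randomised |
|---|---|---|---|---|
| A, no change | before | 91 | 30 | 27 |
| A, no change | on/after | 91 | 30 | 27 |
| B, fall | before | 82 | 33 | 31 |
| B, fall | on/after | 100 | 27 | 22 |

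**Rates under each reading** (before vs on/after). Recruitment rate = recruited / approached. Randomisation rate = randomised / recruited. Each is evaluated within the stated set.

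| Set used | Recruitment, A | Recruitment, B | Randomisation, A | Randomisation, B |
|---|---|---|---|---|
| Randomised men (10.1, 10.3) | 100% vs 100% | 100% vs 100% | 100% vs 100% | 100% vs 100% |
| Recruited men (titles of Tables 6.3, 6.4) | 100% vs 100% | 100% vs 100% | 90.0% vs 90.0% | 93.9% vs 81.5% |
| Approached men, dated by approach | 33.0% vs 33.0% | 40.2% vs 27.0% | 90.0% vs 90.0% | 93.9% vs 81.5% |

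In scenario B the approach-based intervals are 29.6% to 50.9% (33/82) and 18.3% to 35.7% (27/100). The literal populations cannot tell A from B on recruitment rate. The difference they hide is the whole true difference: 0 points in A, 40.2 − 27.0 = 13.2 points in B, and 20 points if acceptance fell from 40% to 20%.

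**Ineligibility.** Among randomised men, Tables 6.5 and 6.6 could hold only men randomised in error. Among recruited men they could also hold men who failed screening after consent, since screening failure is a listed withdrawal reason in Table 2.12. Neither set holds men excluded before consent.

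**If the approached denominator is followed instead.** A man never recruited has no recruitment or randomisation date, and Section 10 supplies no other date for him. An analyst who kept period-specific numerators over the overall number approached would get, in scenario B, 33/182 = 18.1% and 27/182 = 14.8%, in place of 40.2% and 27.0%. To get the right figures, the analyst must supply a rule that the SAP lacks.

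**The case against.** The tempting stronger reading is that the SAP specifies 100% in both periods, with no ineligible men. The documents do not support that. SAP 10.4 and the footnote to Tables 6.3 and 6.4 name men approached as the denominator, and Section 7 includes all men approached. A statistician who followed those would not report 100% against 100%. Among recruited men the randomisation rate can fall below 100%, and post-consent screening failures can appear.

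A reader might also infer that the main-stage decision is compromised. It is not: the Section 11 thresholds apply to the recruitment rate without a split by Covid period, and no threshold is attached to Tables 6.3 to 6.6. Nor is a change in acceptance invisible everywhere. SAP 9.3 and 9.11 already plan graphs of recruitment and randomisation rate over time, and Tables 6.1 and 6.2 count men per open month per centre, which is valid for recruited men.

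These points reduce the concern without removing it. The populations in 10.1 and 10.3 contradict the formula in 10.4, and the approached denominator comes with no dating rule. For Tables 6.5 and 6.6, no footnote brings the approached men back. The footnote to Tables 6.3 and 6.4 is itself at odds with 10.4, because it puts randomisation rate over men approached as well.

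**Conclusion.** The point holds as an internal contradiction in a descriptive section. For recruitment rate and reasons for ineligibility, and in 10.3 for randomisation rate, the stated populations exclude men whom the stated denominator needs. Followed literally, they fix recruitment rate at 100% in both periods, fix randomisation rate at 100% in the randomised set only, and omit men excluded before consent. Followed by denominator, the split is undefined for men never recruited. Either way, the section cannot reliably deliver the comparison in 9.5.

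The 100% results are identities and need no assumption. The 13.2-point example rests on assumed counts and shows only that the full true difference can be lost.

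**What to change.** In SAP 10.1, 10.3 and Tables 6.3 to 6.6:

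- For recruitment rate and reasons for ineligibility, define the population as all men approached before versus on or after 05/03/2020, by approach (screening-log) date.
- For randomisation rate, define it as all men recruited (consented) in each period.
- Correct the footnote to Tables 2.3, 6.3 and 6.4 so that randomisation rate is out of recruited men, as 10.4 states.
- Because SAP 8.3 lists men approached per month and the cut-off falls within March 2020, use individual approach dates or state a rule for that month.

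Tables 6.1 and 6.2 need no change. Nor does the split of consent-to-randomisation time, since randomisation is planned for the consent visit (SAP 6.7.2).

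The cost is SAP wording plus taking approach dates from the screening logs. Protocol 5.1 requires each centre to keep a log but does not say that it records the date of approach, so this should be checked first. No new patient assessments are needed.
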